8.9.3 Adverse events

AEs will be coded using the MedDRA® (version 22.1 or later version) coding system to get a SOC and PT for each AE and will be graded for severity using NCI CTCAE v5.0.

A **TEAE** is defined as any AE with an onset date on or after the first administration of IMP (if the AE was absent before the first administration of IMP (W_pro1 or cemiplimab, whichever comes first)) or worsened after the first administration of IMP (if the AE was present before the first administration of IMP).

AEs with an onset date more than 30 days (after the last administration of W_pro1) or 90 days (90 days after last administration of cemiplimab for Part 2, Arm 1A and Arm 2), respectively, after the last administration of W_pro1 or cemiplimab will be considered as treatment-emergent only if assessed as related to IMP by the investigator. TEAEs will be summarized overall and by treatment group for patients in the safety set.

For patients from Arm 1B who switch to cemiplimab monotherapy, the analysis of AEs will be additionally performed for each IMP separately, (i.e. only TEAEs from the first dose of W_pro1 until last dose of W_pro1 +30 days will be reported as TEAEs for Arm 1B).

In addition, **cemiplimab TEAEs** will be reported in separate AE tables using the subsequent cemiplimab monotherapy on progression set. Cemiplimab TEAEs are defined as TEAEs with an onset date on or after the first dose of cemiplimab until the last dose of cemiplimab +90 days. TEAEs with an onset within the 30 days after last dose of W_pro1 but after start of first cemiplimab treatment will be counted twice, as TEAE for Arm 1B and as cemiplimab TEAE in the respective tables and listings.

AEs started prior to first administration of IMP or AEs after last administration of IMP (follow-up AEs) will be included only in the AE listings.

AEs related to W_pro1

AEs related to W_pro1 are AEs with the item "Causality (relationship to W_pro1)" ticked "*Related*" in "*Adverse Events*" form of the eCRF. If the item is missing, the AE will be considered as related to W_pro1.

AEs related to cemiplimab

AEs related to cemiplimab are AEs with the item "Causality (relationship to cemiplimab)" ticked "*Related*" in "*Adverse Events*" form of the eCRF. If the item is missing, the AE will be considered as related to cemiplimab.

AEs related to IMP (W_pro1 + cemiplimab)

AEs related to IMP are AEs related to either W_pro1 or cemiplimab (or both).

AE leading to permanent study treatment discontinuation (any compound)

AE leading to discontinuation are the AEs with the items “*Action taken with W_pro1*” or “*Action taken with Cemiplimab*” ticked “Trial treatment permanently withdrawn”.

AE leading to dose reduction (any compound)

AE leading to dose reduction are the AEs with the items “*Action taken with W_pro1*” or “*Action taken with Cemiplimab*” ticked “Dose reduced”.

AE leading to dose delay (any compound)

AE leading to dose delay are the AEs with the items “*Action taken with W_pro1*” or “*Action taken with Cemiplimab*” ticked “Trial treatment withdrawn temporarily”.

AE leading to dose modification (any compound)

AE leading to dose modification are the AEs with the items “*Action taken with W_pro1*” or “*Action taken with Cemiplimab*” ticked “Dose reduced” or “Trial treatment withdrawn temporarily”.

Overall summary of treatment-emergent adverse events (TEAEs)

The number and percentage of patients reporting at least one TEAE will be summarized for each of the following AE types:

- Any TEAEs
- TEAEs related to IMP
- TEAEs related to W_pro1
- TEAEs related to Cemiplimab
- Grade ≥ 3 (Maximum intensity) TEAEs
- Grade ≥ 3 TEAEs related to IMP
- Grade ≥ 3 TEAEs related to W_pro1
- Grade ≥ 3 TEAEs related to Cemiplimab
- TEAEs related to trial procedure
- TEAEs related to prostate cancer surgery (Part 2 Arm 2 / Arm 3)
- Any Serious TEAEs
- Serious TEAEs related to IMP

- Serious TEAEs related to W_pro1
- Serious TEAEs related to Cemiplimab
- Serious TEAEs leading to death
- Serious TEAEs leading to death related to IMP
- Serious TEAEs leading to death related to W_pro1
- Serious TEAEs leading to death related to Cemiplimab
- TEAEs leading to IMP dose modification
- TEAEs leading to W_pro1 dose modification
- TEAEs leading to Cemiplimab dose modification
- TEAEs leading to IMP dose reduction
- TEAEs leading to W_pro1 dose reduction
- TEAEs leading to Cemiplimab dose reduction
- TEAEs leading to IMP dose delay
- TEAEs leading to W_pro1 dose delay
- TEAEs leading to Cemiplimab dose delay
- TEAEs leading to permanent discontinuation of IMP
- TEAEs leading to permanent discontinuation of W_pro1
- TEAEs leading to permanent discontinuation of Cemiplimab

For the analysis of Part 1 of the trial, the following AE types will be added in the overall summary of TEAEs:

- DLTs

Analyses of adverse events

The number and percentage of patients for each category above will be summarized by SOC and PT as per MedDRA. If a SOC / PT is reported more than once for a patient, the patient will only be counted once for this SOC / PT. All AE summary tables will be sorted by descending frequency (%) by SOC and by PT within SOC with respect to the Parts 1 and 2 Total column. The number of events will be summarized in the same table.

The following AE tables by SOC and PT will be generated:

- TEAEs by System Organ Class and Preferred Term
- TEAEs related to IMP by System Organ Class and Preferred Term
- TEAEs related to W_pro1 by System Organ Class and Preferred Term

- TEAEs related to Cemiplimab by System Organ Class and Preferred Term
- Grade ≥ 3 (Maximum intensity) TEAEs by System Organ Class and Preferred Term
- Grade ≥ 3 TEAEs related to IMP by System Organ Class and Preferred Term
- Grade ≥ 3 TEAEs related to W_pro1 by System Organ Class and Preferred Term
- Grade ≥ 3 TEAEs related to Cemiplimab by System Organ Class and Preferred Term
- TEAEs related to trial procedure by System Organ Class and Preferred Term
- TEAEs related to prostate cancer surgery (Part 2 Arm 2 / Arm 3) by System Organ Class and Preferred Term
- Any Serious TEAEs by System Organ Class and Preferred Term
- Serious TEAEs related to IMP by System Organ Class and Preferred Term
- Serious TEAEs related to W_pro1 by System Organ Class and Preferred Term
- Serious TEAEs related to Cemiplimab by System Organ Class and Preferred Term
- Serious TEAEs leading to death by System Organ Class and Preferred Term
- Serious TEAEs leading to death related to IMP by System Organ Class and Preferred Term
- Serious TEAEs leading to death related to W_pro1 by System Organ Class and Preferred Term
- Serious TEAEs leading to death related to Cemiplimab by System Organ Class and Preferred Term
- TEAEs leading to IMP dose reduction by System Organ Class and Preferred Term
- TEAEs leading to W_pro1 dose reduction by System Organ Class and Preferred Term
- TEAEs leading to Cemiplimab dose reduction by System Organ Class and Preferred Term
- TEAEs leading to IMP dose delay by System Organ Class and Preferred Term
- TEAEs leading to W_pro1 dose delay by System Organ Class and Preferred Term
- TEAEs leading to Cemiplimab dose delay by System Organ Class and Preferred Term
- TEAEs leading to IMP dose modification by System Organ Class and Preferred Term
- TEAEs leading to W_pro1 dose modification by System Organ Class and Preferred Term
- TEAEs leading to Cemiplimab dose modification by System Organ Class and Preferred Term
- TEAEs leading to permanent discontinuation of IMP by System Organ Class and Preferred Term
- TEAEs leading to permanent discontinuation of W_pro1 by System Organ Class and Preferred Term

- TEAEs leading to permanent discontinuation of Cemiplimab by System Organ Class and Preferred Term

For the analysis of Part 1 of the trial, the following AE tables by SOC and PT will be generated:

- DLTs by System Organ Class and Preferred Term

In addition, the number and percentages of patients reporting the most frequent TEAEs (PT \geq 5% in any treatment group) will be summarized by PT only.

Similar tables to be generated for

- Most frequent TEAEs (\geq 5%) related to IMP by Preferred Term
- Most frequent TEAEs (\geq 5%) related to W_pro1 by Preferred Term
- Most frequent TEAEs (\geq 5%) related to Cemiplimab by Preferred Term

TEAEs by IMP relationship:

The number and percentages of patients with TEAEs will be summarized by relationship to IMP (IMP related and not IMP related) by PT nested within SOC. The worst relationship to IMP will be counted if a TEAE is reported more than once by the same patients for this SOC / PT. Same tables will be generated for TEAEs by relationship to W_pro1 (related to W_pro1 and not related to W_pro1) and by relationship to Cemiplimab (related to Cemiplimab and not related to Cemiplimab).

TEAEs by worst NCI-CTCAE grade:

Moreover, the number and percentage of patients with any TEAE will be summarized by worst NCI CTCAE grade by PT nested within SOC. Only the worst grade will be counted if a TEAE is reported more than once by the same patients for the SOC / PT. The same tables will be generated for TEAEs related to IMP by worst NCI CTCAE grade, TEAEs related to W_pro1 by worst NCI CTCAE grade and TEAEs related to Cemiplimab by worst NCI CTCAE grade.

TEAE table per CT.gov.req:

Moreover, the number and percentage of patients with any non-serious TEAE will be summarized by SOC and PT. A table for non-serious TEAE ($>$ 3% of patients in any treatment arm at the PT level) will be generated .

For patients from Arm 1B who switch to cemiplimab monotherapy, separate AE tables summarizing cemiplimab TEAEs using the safety subsequent cemiplimab monotherapy on progression set will be generated.

Overall summary of cemiplimab TEAEs

The number and percentage of patients reporting at least one cemiplimab TEAE will be summarized for each of the following AE types:

- Any TEAEs
- TEAEs related to Cemiplimab
- Grade ≥ 3 (Maximum intensity) TEAEs
- Grade ≥ 3 TEAEs related to Cemiplimab
- Any serious TEAEs
- Serious TEAEs related to Cemiplimab
- Serious TEAEs leading to death
- Serious TEAEs leading to death related to Cemiplimab
- TEAEs leading to Cemiplimab dose modification
- TEAEs leading to Cemiplimab dose reduction
- TEAEs leading to Cemiplimab dose delay
- TEAEs leading to permanent discontinuation of Cemiplimab

The following AE tables by SOC and PT will be generated for cemiplimab TEAEs:

- TEAEs by System Organ Class and Preferred Term
- TEAEs related to Cemiplimab by System Organ Class and Preferred Term
- Grade ≥ 3 (Maximum intensity) TEAEs
- Grade ≥ 3 TEAEs related to Cemiplimab by System Organ Class and Preferred Term
- Any serious TEAEs by System Organ Class and Preferred Term
- Serious TEAEs related to Cemiplimab by System Organ Class and Preferred Term
- Serious TEAEs leading to death by System Organ Class and Preferred Term
- Serious TEAEs leading to death related to Cemiplimab by System Organ Class and Preferred Term
- TEAEs leading to Cemiplimab dose reduction by System Organ Class and Preferred Term
- TEAEs leading to Cemiplimab dose delay by System Organ Class and Preferred Term
- TEAEs leading to Cemiplimab dose modification by System Organ Class and Preferred Term
- TEAEs leading to permanent discontinuation of Cemiplimab by System Organ Class and Preferred Term

AE listings

All AEs will be listed. Further, all deaths, SAEs, all AEs leading to death, and AEs leading to permanent discontinuation of IMP (W_pro1 and/or cemiplimab) will be listed. Cemiplimab TEAEs in Arm 1B will be flagged in the AE listings.

For Part 1 a listing of DLTs will be generated.

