# **Assessment of Intensity**

The intensity of an AE (i.e., severity of organ toxicity) will be graded according to the NCI CTCAE v5.0. AEs that are not listed in CTCAE v5.0 should be classified according to the investigator's discretion as close as possible to CTCAE v5.0, based on the comparison with the most severe case encountered in past training and clinical experience.

The investigator will make an assessment of intensity for each AE and SAE reported during the trial and assign it to one of the following categories:

- Grade 1 Mild: Asymptomatic or mild symptoms; clinical or diagnostic observations only; intervention not indicated. An event that is easily tolerated by the patient, causing minimal discomfort and not interfering with everyday activities.
- Grade 2 Moderate: Minimal, local or non-invasive intervention indicated; limiting ageappropriate instrumental activities of daily living (ADL)\*. An event that causes sufficient discomfort and interferes with normal everyday activities.
- Grade 3 Severe: Severe or medically significant but not immediately life-threatening; hospitalization or prolongation of hospitalization indicated; disabling; limiting of self-care ADL\*\*. An event that prevents normal everyday activities. An AE that is assessed as severe should not be confused with a SAE. Severe is a category utilized for rating the intensity of an event; and both AEs and SAEs can be assessed as severe.
- Grade 4 Life-threatening consequences; urgent intervention indicated
- Grade 5 Death related to AE

\*\* Self-care ADL refer to bathing, dressing, and undressing, feeding self, using the toilet, taking medications, and not bedridden.

With regards the intensity of an AE the following needs to be documented in source data and eCRF:

- Initial intensity of the AE
- Maximum intensity of the AE
- For each change of intensity:
  - o New grade of intensity
  - Date of change (= start of new grade of intensity)
  - o Time of change (only if relevant)

A change of intensity only needs to be documented if there is a clearly definable change in grading of the AE (e.g., a laboratory result changes from severe to moderate according to CTCAE criteria).

An event is defined as "serious" when it meets at least one of the predefined seriousness criteria as described in the definition of an SAE, NOT when it is rated as severe.

CONFIDENTIAL Page 100 of 122

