8.9.4 Laboratory assessments

Clinical laboratory data to be summarized include hematology, blood chemistry, coagulation, thyroid hormones and urinalysis. The clinical laboratory parameters to be assessed are listed in [Table 8-2](#) and the scheduled time points for assessment are presented in the SoA (see Section [13.6](#)).

All laboratory parameters, except serology assessments, are reported in the clinical database using local safety laboratories. Measurements and corresponding Low and High ranges will be converted into Standard International (SI) units. Values outside the normal ranges are classified as “Not clinically significant” or “Clinically significant” by the investigator.

Serology parameters are analyzed by a central laboratory.

For the derivation of the minimum post-baseline measurement / maximum post-baseline measurement / or worst post-baseline toxicity CTC grades, measurements collected at unscheduled visits will be considered.

The End of Study measurement is defined as last available safety assessment, either at Safety FU D30 or Safety FU D90 Visit (whichever occurs later) or last available safety assessment in case of early trial discontinuation or death. Measurements after switch to cemiplimab monotherapy will not be considered in the derivation of the End of Study measurement.

Clinical laboratory parameters at each scheduled visit and change from baseline to each post-baseline time point will be summarized using descriptive summary statistics for each parameter by treatment group.

The number and percentage of patients reporting markedly abnormal clinical laboratory values as reported by the investigator at any point on the trial will be summarized for each parameter by visit and treatment group using the following categories: Clinically significant low, Low, Normal, High, Clinically significant high.

Shift tables from baseline to Minimum Post-baseline / Maximum Post-baseline and to End of Study measurement with respect to reference range values (Clinically significant low, Low, Normal, High, Clinically significant high) will be generated for each parameter by treatment group.

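### For Arm 1B patients who switch to cemiplimab, an adverse event that is ongoing at the switch and worsens on cemiplimab is missing from every cemiplimab TEAE table, and its peak grade is counted only under Arm 1B

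*SAP*

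**What the plan says.** SAP 8.9.3 has a general TEAE definition and two extra rules for Arm 1B switchers.

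- **General definition.** Besides new events, a TEAE is one that "worsened after the first administration of IMP (if the AE was present before the first administration of IMP". The reference point is whichever IMP came first.
- **Arm 1B (W_pro1) tables, switchers.** "only TEAEs from the first dose of W_pro1 until last dose of W_pro1 +30 days will be reported as TEAEs for Arm 1B".
- **Cemiplimab tables, switchers.** "Cemiplimab TEAEs are defined as TEAEs with an onset date on or after the first dose of cemiplimab until the last dose of cemiplimab" plus 90 days. No worsening criterion is given.
- **Overlap.** "TEAEs with an onset within the 30 days after last dose of W_pro1 but after start of first cemiplimab treatment will be counted twice", once under Arm 1B and once as a cemiplimab TEAE.

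The Grade 3 or higher summaries in SAP 8.9.3 go by maximum intensity. The worst-grade tables take the highest grade per SOC and PT, with no cut at the switch.

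Protocol 10.3.3 (Assessment of Intensity) keeps a change of grade within one AE. It asks for the initial grade, the maximum grade and, for each change, the new grade and "Date of change (= start of new grade of intensity". Protocol 9.4.5 says that Arm 1B AEs are also analysed for each IMP separately and gives the two time windows. It has no rule for an AE that spans the switch.

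**The concern.** The purpose of the extra tables is to separate what happened on W_pro1 from what happened on cemiplimab. Onset-based selection does this for events that begin after the switch, but not for events already ongoing at it. Such events are plausible: the protocol's schedule for the mCRPC arms lets cemiplimab start within 28 days of confirmed progression and allows the W_pro1 end-of-treatment visit to be merged with the first cemiplimab visit.

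More than grade is affected. Seriousness, fatal outcome and action taken with cemiplimab are tabulated over the same onset-selected events. An AE that began mildly on W_pro1, worsened, and led to cemiplimab being stopped would be missing from the table of cemiplimab TEAEs leading to discontinuation.

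The two displays err in opposite directions: Arm 1B looks worse and post-progression cemiplimab looks better. Arm 1B also feeds the pooled monotherapy columns in SAP 13.4. TEAEs by grade and seriousness are a primary endpoint. Safety of cemiplimab after the switch is an exploratory objective.

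**Working it through.** The plan states no figure that depends on this definition, so there is nothing to reproduce. The check applies the written rules to constructed records, then sizes the effect of one patient.

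**Assumed patient.** W_pro1 from day 1 to day 64; cemiplimab from day 92 to day 134. These days are illustrative.

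- Arm 1B window: day 1 to 64 + 30 = day 94.
- Cemiplimab window: day 92 to 134 + 90 = day 224.
- Overlap: days 92 to 94.

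**Rules as written.** An AE enters a set if its onset lies in that set's window. Its grade is its maximum intensity.

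| Record | In Arm 1B tables? | In cemiplimab tables? |
|---|---|---|
| A: onset day 40, Grade 1; Grade 3 from day 100 | Yes (40 ≤ 94), as Grade 3 | No (40 < 92) |
| B: onset day 100, Grade 3 | No (100 > 94) | Yes, as Grade 3 |
| C: onset day 93, Grade 3 | Yes, as Grade 3 | Yes, as Grade 3 |

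B and C behave as the SAP intends. A does not: its Grade 3 period lies wholly on cemiplimab and after the W_pro1 window has closed, yet it appears only under Arm 1B.

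No other rule rescues record A. The general worsening clause compares with the period before first W_pro1, when the event did not exist. The double-counting rule needs an onset after cemiplimab has started.

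**Same records under the proposed rule** (onset or grade increase on or after first cemiplimab; Arm 1B grade capped at last W_pro1 dose + 30 days):

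- A: maximum grade up to day 94 is 1, so it is a Grade 1 TEAE in Arm 1B. Day 100 lies within 92 to 224 and Grade 3 exceeds Grade 1, so it is a Grade 3 cemiplimab TEAE.
- B and C: unchanged.
- If A had instead worsened on day 93, inside the overlap, it would be Grade 3 in both sets, in line with the SAP's treatment of overlap onsets.

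**Size.** The tables count patients, so one misallocated AE changes a rate by at most 1/N:

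- Arm 1B: 1/33 = 3.0 points (planned maximum) to 1/20 = 5.0 points (first stage).
- Cemiplimab set: 1/20 = 5 points, 1/10 = 10 points, 1/5 = 20 points, for an assumed 20, 10 or 5 switchers.

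**The case against.** Several points on the other side are sound.

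- **Maximum intensity is used on both sides.** A reader might infer that the SAP grades W_pro1 events by maximum intensity and cemiplimab events by something else. It does not: SAP 8.9.3 lists Grade 3 or higher by maximum intensity for the cemiplimab tables too. The fault is the onset filter, together with the absence of a grade cut-off for Arm 1B.
- **Laboratory data.** SAP 8.9.4 says "Measurements after switch to cemiplimab monotherapy will not be considered in the derivation of the End of Study measurement" and does not repeat this for minimum, maximum or worst grade. A reader might infer that post-switch values leak into those summaries. SAP 8.1 sends Arm 1B safety data other than AEs collected after the switch to listings, so the documents do not support that reading.
- **Late related events.** The cemiplimab definition has no extension for related events beyond 90 days. A reader might infer that the SAP dropped it. Protocol 9.4.5 sets the same window for Arm 1B, and the W_pro1 window for switchers is closed in the same way, so this is not a departure.
- **Attribution.** Causality is recorded separately for each product and all AEs are listed, so the event is not lost and need not be labelled as related to W_pro1. But its row in a cemiplimab-related table would still sit in the Arm 1B column, and the listings flag only events that meet the onset-based definition.
- **Frequency.** The event must start on W_pro1, persist to the switch and then worsen. Protocol 2.3 describes related BNT112 events as transient, and Protocol 8.4.7 excludes disease progression as such from AEs. Nothing in the documents shows that the pattern is common.
- **Descriptive use.** No hypothesis or decision rule rests on these rates.

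The last two points limit the size and weight of the problem. They do not remove the misallocation.

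**Conclusion.** The point holds in this limited form. Under the written rules, an AE ongoing at the switch that worsens on cemiplimab is excluded from all cemiplimab TEAE tables and counted at its maximum grade only under Arm 1B. This works against the plan's own aim of analysing AEs for each IMP separately.

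The shifts of 3 to 5 points in Arm 1B and 5 to 20 points in the cemiplimab set are upper bounds per affected patient. They apply only if that patient has no other qualifying event in the same row. The Arm 1B denominators are planned numbers, and the number of switchers is assumed. The total effect cannot be computed, because the documents give neither the number of switchers nor any AE rates. The conclusion also assumes that sites follow Protocol 10.3.3; a site that opened a new AE record at worsening would give it a new onset date, and the event would be captured.

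This is worth correcting because it touches a primary endpoint and the remedy is cheap.

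**What to change.** Amend SAP 8.9.3 in two places.

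1. **Cemiplimab TEAEs:** AEs with onset, or with a first increase in grade over the pre-cemiplimab level, on or after the first cemiplimab dose and up to the last cemiplimab dose plus 90 days. Use the recorded dates of intensity change.
2. **Arm 1B (W_pro1) tables for switchers:** take the maximum grade reached up to the last W_pro1 dose plus 30 days. This matches the existing window and keeps the deliberate double counting in the overlap. Cutting at first cemiplimab instead would undo that choice and could hide delayed W_pro1 toxicity, so the SAP should state this one cut-off only.

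The cost is SAP wording and one further derivation from intensity-change records that the protocol already requires in the eCRF; no new data are needed. Some AEs will appear in both sets. Seriousness, outcome and action taken belong to the AE as a whole, so the grade cap does not remove them from Arm 1B; a footnote should say so.

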#### **AEs**

AEs will be coded using the most recent version of MedDRA® coding system to get a SOC and PT for each AE and graded for severity using NCI CTCAE v5.0.

A TEAE is defined as any AE with an onset date on or after the first administration of IMP (if the AE was absent before the first administration of IMP) or worsened after the first administration of IMP (if the AE was present before the first administration of IMP). AEs with an onset date more than 30 days or 90 days, respectively for BNT112 or cemiplimab, after the last administration of IMP will be considered as treatment-emergent only if assessed as related to the IMP by the investigator. TEAEs will be summarized overall and by treatment arm.

For Arm 1B, the analysis of AEs will be additionally performed for each IMP separately, i.e. TEAEs from first dose of BNT112 until last dose of BNT112 +30 days and TEAEs from first dose of cemiplimab until last dose of cemiplimab +90 days, respectively.

The number and percentage of patients reporting at least one AE will be summarized by PT nested within SOC for each of the following AE types:

- Any AE
- Related AE
- Grade ≥3 AE
- Related Grade≥3 AE
- Any SAE
- Related SAE
- SAE leading to death
- AEs leading to dose delays or dose reduction
- AE leading to permanent discontinuation-of-treatment

Moreover, the number and percentage of patients with any AE will be summarized by worst NCI CTCAE grade by PT nested within SOC.

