# 10.3.3. Recording and Follow-Up of AE and/or SAE

### **AE and SAE Recording**

The investigator needs to assess and document any AE regardless of association with the use of the trial treatment during the period of observation (from signing ICF until FU-D30 for Part 1 and Part 2 Arm 1B and Arm 3, and FU-D90 visit for Part 2 Arm 1A, Arm 1B switch-over patients, and Arm 2).

- Data pertaining to AEs will be collected during each trial visit either. Based on the patient's spontaneous description or investigator's inquiry or discovered in the course of examinations done during the visit, clinical significance of any sign or symptom needs to be evaluated by the investigator.
- Clinically significant findings need to be documented as AEs in the source data and eCRF. Findings that are evaluated and documented in the source data as not clinically significant (e.g., an abnormal laboratory value without any clinical manifestation), should not be documented as AE.
- The investigator will then record all relevant AE information in the eCRF and perform an assessment on:
  - o Intensity according to CTCAE v5.0
  - Seriousness
  - Outcome
  - O Drug relationship of the AE to the trial treatment
  - o Any trial treatment action and/or any other action taken
- All assessments as well as AE term (diagnosis/description), start date and time of onset, end date and time need to be documented on the source data and eCRF.
- It is not acceptable for the investigator to send photocopies of the patient's medical records to the sponsor in lieu of completion of the AE eCRF page.
- There may be instances when copies of medical records for certain cases are requested by the sponsor. In this case, all patient identifiers, with the exception of the patient number, will be redacted on the copies of the medical records before submission to the sponsor.
- To avoid colloquial expressions, the AE should be reported in standard medical terminology. The investigator will attempt to establish a diagnosis of the event based on signs, symptoms, and/or other clinical information. Whenever possible, the diagnosis (not the individual signs/symptoms) will be documented as the AE. If a definitive diagnosis is not possible, the individual signs and symptoms should be recorded.

CONFIDENTIAL Page 99 of 122

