Time from treatment start to post treatment prostatectomy for LPC patients (in days):

For date of prostatectomy or radical prostatectomy, missing day will be replaced with the first day of the month. In case month is not reported, missing month will be replaced with July.

Time from treatment start to prostatectomy (days) will be calculated as:

(Date of prostatectomy – date of first IMP administration (W_pro1 or cemiplimab) + 1

Study day:

Study day is defined as follows:

If date of assessment is on or after the date of first IMP administration (W_pro1 or cemiplimab):

- Date of assessment – date of first IMP administration + 1

If date of assessment is before date of first IMP administration (W_pro1 or cemiplimab):

- Date of assessment – date of first IMP administration

Laboratory values with “< xx” or “> xx”:

Any laboratory values given as “< xx” or “> xx” in the database will be imputed with the numeric value of xx without the sign for the descriptive statistics and the calculation of changes from baseline (e.g., a value of < 1 will be imputed as 1 for the calculations).

Last date known to be alive:

Last date known to be alive is defined as last documented date in the database for the patient, including all visit dates, assessment dates (if different from visit dates), trial treatment administration dates, tumor assessment dates, end of treatment dates, date of trial completion or early trial withdrawal date, start/stop dates of AEs, PSA response date, survival follow-up date (where patients survival status is alive), whichever comes last.

Start of Follow-up Period:

Part 1 and Part 2 mCRPC patients: Follow-up period starts at the administration of the last dose of IMP.

Part 2 LPC patients: Follow-up period starts at the last administration of IMP at Cycle 8 or at administration of the last IMP in case of discontinuation of trial treatment.

Pooling of centers:

No pooling of centers is planned for this trial.

Conventions for imputing missing/partially missing dates:

When computations on dates are to be performed, incomplete/missing dates will be imputed using the following rules.

- Missing day, month/year present: If the month/year is the same as the month/year of the first IMP administration date, then impute missing start dates with first IMP administration date. Otherwise, for dates corresponding to a start date, impute with the first day of the month and, for dates corresponding to a stop date, impute with the last day of the month.

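### SAP 8.9.3 sends AEs with onset before first dose or after last dose to listings only, which contradicts its own TEAE definition for three groups of events

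*SAP*

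**What the plan says.** Occurrence of TEAEs is a primary endpoint in both parts (protocol 3 and 9.4.2; SAP 8.9.1).

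SAP 8.9.3 defines a TEAE as an AE with onset on or after first IMP, "or worsened after the first administration of IMP (if the AE was present before the first administration of IMP"). Protocol 9.4.5 has the same definition. It closes the window by saying that "AEs with an onset date more than 30 days or 90 days, respectively for BNT112 or cemiplimab, after the last administration of IMP" count only if the investigator judges them related. Onset inside 30 or 90 days therefore counts whatever the causality.

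For Arm 1B patients who switch, SAP 8.9.3 tabulates AEs separately for each drug: W_pro1 events to last W_pro1 dose plus 30 days, and cemiplimab TEAEs, defined as "TEAEs with an onset date on or after the first dose of cemiplimab until the last dose of cemiplimab +90 days".

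The next paragraph of SAP 8.9.3 then says that AEs that began before first IMP or "AEs after last administration of IMP (follow-up AEs) will be included only in the AE listings".

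SAP 8.2 defines the start of follow-up. For mCRPC patients, "Follow-up period starts at the administration of the last dose of IMP". In the LPC arms, "Follow-up period starts at the last administration of IMP at Cycle 8 or at administration of the last IMP in case of discontinuation". SAP 13.1, which lists departures from the protocol's analyses, mentions no change to the AE analysis.

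**The concern.** A programmer who works from SAP 8.9.3 has two instructions for the same events. One puts them in the TEAE tables and the other keeps them out. If the second were followed, the tables that report a primary endpoint would omit events that the protocol collects and counts. Protocol 10.3.3 requires AE recording "during the period of observation (from signing ICF until FU-D30 for Part 1 and Part 2 Arm 1B and Arm 3", and to FU-D90 for Arm 1A, Arm 2 and the switch patients. The post-dose part of that period would disappear from the tables.

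The omission would also be uneven. The window after last dose is 90 days where cemiplimab is given and 30 days where it is not, so combination arms would lose more. SAP 13.4 plans combined AE columns for monotherapy and for combination therapy, and these would be affected differently.

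**Working it through.** No figure in the plan needs reproducing. The first step is to run each kind of AE through both rules.

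| AE | TEAE definition (SAP 8.9.3, protocol 9.4.5) | Listing-only sentence | Result |
|---|---|---|---|
| Onset before first dose, no worsening | Not a TEAE | Listing only | Agree |
| Onset before first dose, worsens after it | TEAE | Listing only | Conflict |
| New onset between first and last dose | TEAE | Not affected | Agree |
| Onset after last dose, within 30/90 days | TEAE, any causality | Listing only | Conflict |
| Onset beyond 30/90 days, related | TEAE | Listing only | Conflict |
| Onset beyond 30/90 days, unrelated | Not a TEAE | Listing only | Agree |

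Three points decide whether the conflicts are real.

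- **Worsening.** Protocol 10.3.3 has a change of intensity recorded within the AE, with "Date of change (= start of new grade of intensity"). A worsened AE can therefore keep a start date before first dose and be caught by the sentence.
- **The meaning of follow-up.** If follow-up began at day 30 or day 90, the post-dose half of the sentence would largely agree with the definition. SAP 8.2 starts it at the last dose.
- **Switch patients.** Their last cemiplimab dose is their last IMP dose. The 90 days after it that the cemiplimab TEAE tables are meant to cover lie wholly after last IMP.

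The second step is the share of the TEAE window that lies after last dose. Cycles are 21 days (protocol 6), so a last dose on Day 1 of cycle c falls d = 21 × (c − 1) days after first dose. With a post-dose window of w days, share = w / (d + w). Where both drugs are given, their last doses are taken to fall on the same day.

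| Last dose | d | w = 90 | w = 30 |
|---|---|---|---|
| C8D1, LPC, planned last dose (protocol 4.1) | 7 × 21 = 147 | Arm 2: 90/237 = 38.0% | Arm 3: 30/177 = 16.9% |
| C3D1, mCRPC, assumed | 2 × 21 = 42 | Arm 1A: 90/132 = 68.2% | Part 1, or Arm 1B without switch: 30/72 = 41.7% |
| C12D1, mCRPC, assumed | 11 × 21 = 231 | Arm 1A: 90/321 = 28.0% | Part 1, or Arm 1B without switch: 30/261 = 11.5% |

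C3D1 is the last dose before the first scheduled scan at C3D15. C12D1 stands for longer treatment, since mCRPC treatment has no fixed end. Counting C1D1 as day 1 instead of day 0 moves each share by less than one percentage point.

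The third step is the surgery table. Protocol 8.3.3 places prostatectomy after the EoT visit, hence after last dose. Suppose that surgery follows directly on an EoT visit held 21 days after last dose, the latest day that the protocol 1.4 footnote allows. The TEAE definition then leaves 90 − 21 = 69 days for surgical AEs in Arm 2 and 30 − 21 = 9 days in Arm 3, whatever their relation to IMP. The listing-only sentence leaves none, so Table 14.3.1.11 would be empty for these patients.

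**The case against.** The best defence is that one loose sentence should not be read against everything around it. The same section says that TEAEs will be summarized by group, gives Arm 1B its 30 days, and orders cemiplimab TEAE tables to 90 days. Apart from the Part 1 DLT displays, the planned AE tables are tables of TEAEs, and Table 14.3.1.11 makes little sense unless post-dose AEs are tabulated. The reading that fits all of this is that AEs which are not TEAEs go to listings. The term for AEs in follow-up is nowhere defined, and SAP 8.5 uses the start of follow-up for disposition. This stands as evidence of intent. It does not remove the contrary instruction, and the one definition of follow-up in the SAP points the other way.

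The pre-dose conflict is also narrow. It covers only AEs with onset between consent and first dose that later worsen. Exacerbation of a condition that predates the trial is itself an AE under protocol 10.3.1 and can have its onset after first dose.

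A reader might infer more than the documents support:

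- *That 38% or 68% of TEAEs would be lost.* The shares are of calendar days, and the documents give no event counts. SAP 8.9.3 counts a patient once per preferred term, so a percentage falls only if the term occurs in that patient solely among the excluded events. Protocol 2.3 describes the AEs typical of this vaccine class as transient.
- *That safety events would vanish.* SAP 8.9.3 lists all AEs, with separate listings for deaths, SAEs and AEs leading to death or discontinuation.
- *That the primary endpoint was narrowed on purpose.* SAP 13.1 declares no such change.

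**Conclusion.** The contradiction is real and sits inside one SAP section, as well as between that section and protocol 9.4.5. It concerns exactly three groups: pre-dose AEs that worsen after first dose, AEs with onset within 30 days of last W_pro1 or 90 days of last cemiplimab, and later AEs related to IMP.

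The effect is conditional. If the listing-only sentence were applied literally, TEAE incidence would be understated by an amount that cannot be given in events. In calendar days, the part of the window affected is 38% in Arm 2 and 17% in Arm 3 for a last dose at C8D1. For mCRPC, with assumed last doses from C3D1 to C12D1, it runs from 68% down to 28% with the 90-day window and from 42% down to 11.5% with the 30-day window. The documents do not show that the tables will be wrong: the table shells are in a separate document and may already follow the TEAE definition. The sentence should be corrected because it governs a primary endpoint and, as written, gives the wrong result.

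**What to change.** Replace the listing-only sentence in SAP 8.9.3 with:

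> AEs that do not meet the TEAE definition appear in the AE listings only. These are AEs with onset before first IMP and no worsening after first IMP, and AEs not related to IMP with onset more than 30 days after last W_pro1 and, for patients who received cemiplimab, more than 90 days after last cemiplimab.

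Add one statement for Arm 1B switch patients. The per-drug analyses stop at W_pro1 plus 30 days and cemiplimab plus 90 days, yet a related AE with later onset still meets the general definition. The SAP should name the table in which it is counted.

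If the exclusion was in fact intended, it has to be reconciled with protocol 9.4.5 and declared in SAP 13.1.

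The cost is one replaced sentence and one added statement, with no new data and no new table. The shells and programs need a check against the TEAE definition; if they already follow it, only the SAP wording changes.
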